## 8.3 ADVERSE EVENTS AND SERIOUS ADVERSE EVENTS

### 8.3.1 DEFINITION OF ADVERSE EVENTS (AE)

An adverse event (AE) is any untoward medical occurrence in a subject during participation in the clinical study or with use of the experimental agent being studied.

### 8.3.2 DEFINITION OF SERIOUS ADVERSE EVENTS (SAE)

A serious adverse event (SAE) is one that meets one or more of the following criteria:

- Results in death
- Is life-threatening (places the subject at immediate risk of death from the event as it occurred)
- Results in inpatient hospitalization or prolongation of existing hospitalization
- Results in a persistent or significant disability or incapacity or substantial disruption of the ability to conduct normal life functions
- Results in a congenital anomaly or birth defect

An important medical event that may not result in death, be life threatening, or require hospitalization may be considered an SAE when, based upon appropriate medical judgment, the event may jeopardize the subject and may require medical or surgical intervention to prevent one of the outcomes listed in this definition.

### 8.3.3 CLASSIFICATION OF AN ADVERSE EVENT

#### 8.3.3.1 SEVERITY OF EVENT

The following scale will be used to grade adverse events:

1. **Mild:** no intervention required; no impact on activities of daily living (ADL)
2. **Moderate:** minimal, local, or non-invasive intervention indicated; moderate impact on ADL
3. **Severe:** significant symptoms requiring invasive intervention; subject seeks medical attention, needs major assistance with ADL

#### 8.3.3.2 RELATIONSHIP TO STUDY INTERVENTION

All adverse events (AEs) must have their relationship to study intervention assessed by the clinician who examines and evaluates the participant based on temporal relationship and his/her clinical judgment.

The degree of certainty about causality will be graded using the categories below.

- **Definitely Related** – There is clear evidence to suggest a causal relationship, and other possible contributing factors can be ruled out. The clinical event, including an abnormal laboratory test result, occurs in a plausible time relationship to study intervention administration and cannot be explained by concurrent disease or other drugs or chemicals. The response to withdrawal of the study intervention (de-challenge) should be clinically plausible. The event must be pharmacologically or phenomenologically definitive, with use of a satisfactory rechallenge procedure if necessary.
- **Probably Related** – There is evidence to suggest a causal relationship, and the influence of other factors is unlikely. The clinical event, including an abnormal laboratory test result, occurs within a reasonable time after administration of the study intervention, is unlikely to be attributed to

concurrent disease or other drugs or chemicals, and follows a clinically reasonable response on withdrawal (dechallenge). Rechallenge information is not required to fulfill this definition.

- **Potentially Related** – There is some evidence to suggest a causal relationship (e.g., the event occurred within a reasonable time after administration of the trial medication). However, other factors may have contributed to the event (e.g., the participant's clinical condition, other concomitant events). Although an AE may rate only as "possibly related" soon after discovery, it can be flagged as requiring more information and later be upgraded to "probably related" or "definitely related", as appropriate.
- **Unlikely to be related** – A clinical event, including an abnormal laboratory test result, whose temporal relationship to study intervention administration makes a causal relationship improbable (e.g., the event did not occur within a reasonable time after administration of the study intervention) and in which other drugs or chemicals or underlying disease provides plausible explanations (e.g., the participant's clinical condition, other concomitant treatments).
- **Not Related** – The AE is completely independent of study intervention administration, and/or evidence exists that the event is definitely related to another etiology. There must be an alternative, definitive etiology documented by the clinician.]

### 8.3.3.3 EXPECTEDNESS

The PI and/or study physician will be responsible for determining whether an adverse event (AE) is expected or unexpected. An AE will be considered unexpected if the nature, severity, or frequency of the event is not consistent with the risk information previously described for the intervention. This study includes administration of transdermal estrogen. According to the package insert, expected risks when administering estrogens include the list below.

Less common but serious:

- Breast cancer
- Cancer of the uterus
- Stroke
- Heart attack
- Blood clots
- Dementia
- Gallbladder disease
- Ovarian cancer

Warning signs of serious side effects:

- Breast lumps
- Unusual vaginal bleeding
- Dizziness and faintness
- Changes in speech
- Severe headaches
- Chest pain
- Shortness of breath
- Pains in your legs
- Changes in vision
- Vomiting

Common side effects:

- Headache
- Breast pain
- Irregular vaginal bleeding or spotting
- Stomach/abdominal cramps, bloating
- Nausea and vomiting
- Hair loss

Other side effects:

- High blood pressure
- Liver problems
- High blood sugar
- Fluid retention
- Enlargement of benign tumors of the uterus (“fibroids”)
- Vaginal yeast infection

It is worth noting that these are risks for administration of any estrogens and for long duration. Many of these risks were established from the Women’s Health Initiative Study, a landmark study that used long-term oral administration of conjugated equine estrogens. Reported risks from research using short-term administration of transdermal estradiol have been minimal.

#### 8.3.4 TIME PERIOD AND FREQUENCY FOR EVENT ASSESSMENT AND FOLLOW-UP

The occurrence of an adverse event (AE) or serious adverse event (SAE) may come to the attention of study personnel during study visits and interviews of a study participant presenting for medical care, or upon review by a study monitor.

All AEs including local and systemic reactions not meeting the criteria for SAEs will be captured on the appropriate case report form (CRF). Information to be collected includes event description, time of onset, clinician’s assessment of severity, relationship to study product (assessed only by those with the training and authority to make a diagnosis), and time of resolution/stabilization of the event. All AEs occurring while on study must be documented appropriately regardless of relationship. All AEs will be followed to adequate resolution.

Any medical condition that is present at the time that the participant is screened will be considered as baseline and not reported as an AE. However, if the study participant’s condition deteriorates at any time during the study, it will be recorded as an AE.

Changes in the severity of an AE will be documented to allow an assessment of the duration of the event at each level of severity to be performed. AEs characterized as intermittent require documentation of onset and duration of each episode.

Study staff will record all reportable events with start dates occurring any time after informed consent is obtained until 7 (for non-serious AEs) or 30 days (for SAEs) after the last day of study participation. At each study visit, study staff will inquire about the occurrence of AE/SAEs since the last visit. Events will be followed for outcome information until resolution or stabilization.

#### 8.3.5 ADVERSE EVENT REPORTING

Any major AE, i.e., any serious injury including all SAEs that are unanticipated, serious, and possibly related to the study intervention will be recorded and reported to the PI immediately after completing any and all actions that are necessary to protect the subject's health and safety. A description of the event and the date and location of the event will be recorded on the AE Reporting Form. Reported events will be compiled to submit to the IRB and NIA annually, unless it is a serious event that requires more immediate reporting.

- Unexpected fatal or life-threatening AEs related to the intervention will be reported to the IRB and NIA within 3 days of the investigator becoming aware of the event. Other serious and unexpected AEs related to the intervention will be reported within 7 days.
- Anticipated or unrelated SAEs will be handled in a less urgent manner but will be reported to the IRB and NIA on an annual basis.
- All other AEs documented during the course of the trial will be reported to the IRB and NIA on an annual basis by way of inclusion in the annual report.

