### 5.4 STRATEGIES FOR RECRUITMENT AND RETENTION

This single-site study aims to recruit 10 postmenopausal women with type 2 diabetes and 10 postmenopausal without type 2 diabetes. All women should be between the ages of 60-80 years and may be of any race or ethnicity. In the Winston-Salem, Forsyth County region, which is the catchment area for this study, approximately 25% of people in this age range identify as minority (primarily African America, less than 1% identify as Hispanic ethnicity). To reflect these demographics, we aim to include 2-3 African American women in each arm of the study.

We anticipate enrolling 1-2 women per month and screening up to 200 women to reach enrollment. Women will be recruited through fliers posted in the general public, hospital, and outpatient clinics; physician outreach in outpatient clinics; advertisement through the VITAL newsletter of the Section on Gerontology and Geriatric Medicine; community talks given by the PI or study staff; and word-of-mouth. Recruitment venues include Wake Forest Baptist Health and Wake Forest School of Medicine clinics, and public venues such as the YMCA, community centers, or churches. Recruitment of historically under-represented populations, such as African American women, will be accomplished through outreach to the African American community through our Aging Center and engagement of historically African American churches in the area. The Aging Center has a strong history of enrolling 25% or more African American participants in research studies.

Study retention will be facilitated by compensating participants for study visits and through weekly contact with the study coordinator to ensure safety and compliance.

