#### 10.1.6 SAFETY OVERSIGHT

Safety oversight will be monitored by the PI and the study physician, as well as the study team. Any safety concerns should be reported immediately to the PI and/or study physician or proxy for the study physician. Safety concerns will also be addressed at monthly study team meetings. AEs will be reported as described above.

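### Sections 8.3.3.3 and 8.3.5 are not reconciled: by default, a related SAE on the package-insert list reaches the IRB and NIA only in the annual report

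*Combined protocol and SAP*

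**What the plan says.** **Reporting clocks (8.3.5).** Unexpected, related events that are fatal or life-threatening go to the IRB and NIA within 3 days. Other serious, unexpected, related events go within 7 days. For the rest, "Anticipated or unrelated SAEs will be handled in a less urgent manner" and are reported annually. The sentence before these bullets allows an exception to annual reporting for a serious event that needs faster reporting, but does not define it.

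**Expectedness (8.3.3.3).** The reference is stated as follows: "According to the package insert, expected risks when administering estrogens include the list below". Under the label "Less common but serious" the list names breast, uterine and ovarian cancer, stroke, heart attack, blood clots, dementia and gallbladder disease. The section then qualifies the list: "It is worth noting that these are risks for administration of any estrogens and for long duration". It adds that reported risks with short-term transdermal estradiol have been minimal. The general test is "An AE will be considered unexpected if the nature, severity, or frequency of the event is not consistent with the risk information previously described", and "The PI and/or study physician will be responsible for determining whether an adverse event (AE) is expected or unexpected".

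**Known risks (2.3.1).** The short-term effects given are nausea, breast tenderness, spotting and bleeding. Thrombosis, uterine cancer and breast cancer appear under use lasting several years.

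**Oversight (10.1.6).** "Safety oversight will be monitored by the PI and the study physician, as well as the study team". The amendment history (10.3) says that the study has no data safety monitoring board.

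**The concern.** The two sections work from different ideas of what is expected. Section 8.3.3.3 supplies a list and says in the same place that it describes a different exposure: any estrogen, used for a long time. Section 8.3.5 then makes expectedness the switch between reporting within days and reporting once a year. The clause that sends SAEs to the annual report joins anticipated and unrelated with an "or", so an anticipated SAE goes there even when it is judged related.

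What is at stake is how soon anyone outside the study team learns of a related stroke, clot or infarction. Section 2.3.2 anticipates no benefit to participants. Women are screened for earlier clots, stroke and myocardial infarction (8.1), so such an event during the patch course would be notable. The people who decide expectedness are also the people who carry safety oversight.

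**Working it through.** The protocol gives no figure for enrolment at the time of an annual report, so there is none to reproduce. The check has two parts.

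**1. Tracing a related, listed SAE (for example a blood clot during week 5 of the patch)**

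- 8.3.3.3: the event is on the expected list, so it counts as expected unless the PI or study physician finds that its nature, severity or frequency does not fit the described risk. The list gives no severities, frequencies or durations to compare with.
- 8.3.5, 3-day and 7-day bullets: both require the event to be unexpected, so neither applies.
- 8.3.5, anticipated SAEs: the event falls here, whatever its relatedness. Reporting is annual.
- 8.3.5, exception for serious events: undefined, and the bullets that follow again require unexpectedness.
- 8.4, unanticipated problems: unexpectedness is one of three criteria that must all be met.
- 10.1.9, prompt reporting: covers unanticipated problems and SAEs that are serious and unexpected. Its mention of Study Reports for a DSMB gives no timing for individual events.

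The default route is the annual report.

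**2. Size of the delay in women enrolled**

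Inputs: N = 10 + 10 = 20 (4.1); "We anticipate enrolling 1-2 women per month" (5.4), so the rate r is 1 to 2; annual interval of 12 months (8.3.5).

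- Accrual time = N / r: 20/2 = 10 months and 20/1 = 20 months. Adding 14-18 weeks for the last participant (about 3.2-4.1 months) gives about 13.2-24.1 months, which is compatible with the 24-36 months in section 1.1 that also cover the primary analyses.
- Women enrolled during a wait of w months, with enrolment open = min(20, r × w).

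| Wait | r = 1 | r = 2 |
|---|---|---|
| 7 days (7/30.4 month) | 0.23 | 0.46 |
| 6 months | 6 (30%) | 12 (60%) |
| 12 months | 12 (60%) | min(20, 24) = 20 (100%) |

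The 6-month row is the average wait if the event is equally likely at any time in the interval. At 2 a month enrolment closes at month 10, so the full 12 women are reached only if the event occurs by month 4 (20 − 2 × 4 = 12).

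The 12-month row is a ceiling: it counts a whole interval, not enrolment after an event. As an example with an event at month 2 and a report at month 12, the women enrolled in between number 12 − 2 = 10 at 1 a month and 20 − 4 = 16 at 2 a month.

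**The case against.** The strongest reply is that the list does not settle expectedness by name alone. The test of nature, severity or frequency, read with the caveat about long duration, would let the PI or study physician class a stroke in an 8-week transdermal course as unexpected, and the 3-day or 7-day clock would start. This stands. A reader might infer that a listed event must wait for the annual report, and the text does not support that. It supports a default that can be departed from by discretion without stated guidance.

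Other points in reply:

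- Section 8.4.1 judges unexpectedness against all protocol-related documents and the population studied. In women screened for thrombosis, a clot within 8 weeks could be argued to qualify as an unanticipated problem. This is possible, but it again turns on a judgement of unexpectedness.
- A reader might infer that the PI would not hear promptly of a listed SAE. The documents do not support this. The immediate-reporting clause in 8.3.5 covers serious injuries and names one class of SAE as included, not as the only class. Section 10.1.6 sends any safety concern at once to the PI and/or study physician.
- A reader might infer that enrolment would simply continue for a year. Section 10.1.2 allows suspension for significant risk, whether or not it is unexpected, and then requires prompt notice to the IRB and NIA. That power is discretionary and sets no reporting clock for a single event.
- Tying prompt reporting to unexpected and related events matches the OHRP criteria set out in 8.4.1. The structure is therefore a legitimate design choice. The weakness is the reference list placed inside it.

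**Conclusion.** The point holds as a failure to reconcile 8.3.3.3 (and 2.3.1) with 8.3.5. By default, a related SAE on the package-insert list reaches the IRB and NIA only in the annual report, although the protocol itself says that the list reflects a different exposure. Earlier reporting depends on an unguided test or an undefined exception, both in the hands of the study team.

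The size is about 6-12 women (30-60% of 20) enrolled during an average 6-month wait, and 12-20 (60-100%) over a full 12-month interval, against less than one under the existing 7-day clock. These figures assume the protocol's accrual rate, enrolment that stays open through the wait (up to the target of 20), and a report date that the documents do not give. It would be tempting to read 60-100% as the share enrolled after an event; it is only an upper limit. Nor does the argument need the participants to be healthy volunteers: ten of the 20 are to have type 2 diabetes (4.1).

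This is a cheap improvement to outside oversight. It does not affect the validity of the analysis.

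**What to change.** In 8.3.5, apply the existing 3-day and 7-day clocks to every SAE graded potentially, probably or definitely related in 8.3.3.2, whether or not it is on the package-insert list. Keep annual reporting for unrelated SAEs.

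Alternatively, state in 8.3.3.3 that expectedness is judged against the short-term effects described in 2.3.1. This would bring a related stroke, clot, infarction or cancer under the existing clocks. It is narrower, because a related SAE of a kind named among the short-term effects could still be classed as anticipated. If the first change is made, the second is not needed for the clocks to work.

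Either change is a matter of amendment wording and alters no procedure, visit or analysis. The cost is at most a few more expedited reports in a study of 20 women.

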#### 8.3.6 REPORTING EVENTS TO PARTICIPANTS

During the consenting process, incidental findings will be explained to the participant. Participants will be informed that incidental findings may reveal a previously unknown health concern that it would benefit the participant to know about so that they can seek treatment. However, because the tests we are performing are for research and not diagnostic purposes, incidental findings may not reflect a real problem if a diagnostic scan is performed later. In this case, incidental findings can lead to unnecessary testing.

Participants will be informed of study-related results under the following circumstances.

- If a participant does not qualify for the study at screening, they will be informed why they did not qualify. If they did not qualify because a screening measure was out of range and may indicate an underlying health concern (incidental finding), that will be explained. The nature of incidental findings will also be reviewed with the participant.
- When MRI scans are viewed for research purposes, incidental findings may be observed. In some cases, incidental findings may reveal a previously unknown health concern that it would benefit the participant to know about so that they can seek treatment. However, in our experience, some people do not wish to be informed of MRI-related incidental findings. Therefore, during consent, participants will be asked if they wish to be informed of MRI-related incidental findings. All of our MRI scans will be read by a board-certified neuroradiologist regardless to rule out major abnormalities or issues that might lead to scans being excluded from the study. If an incidental finding is noted and the participant has requested to be notified, we will contact them and provide the feedback from the neuroradiologist. At the participant's request, we will share the research MRI scans with their physician.

#### 8.3.7 REPORTING OF PREGNANCY

All women in the study will be postmenopausal.

### 8.4 UNANTICIPATED PROBLEMS

#### 8.4.1 DEFINITION OF UNANTICIPATED PROBLEMS (UP)

The Office for Human Research Protections (OHRP) considers unanticipated problems involving risks to participants or others to include, in general, any incident, experience, or outcome that meets all of the following criteria:

- Unexpected in terms of nature, severity, or frequency given (a) the research procedures that are described in the protocol-related documents, such as the Institutional Review Board (IRB)-approved research protocol and informed consent document; and (b) the characteristics of the participant population being studied;
- Related or possibly related to participation in the research (“possibly related” means there is a reasonable possibility that the incident, experience, or outcome may have been caused by the procedures involved in the research); and
- Suggests that the research places participants or others at a greater risk of harm (including physical, psychological, economic, or social harm) than was previously known or recognized.

#### 8.4.2 UNANTICIPATED PROBLEM REPORTING

The PI and study staff will report unanticipated problems (UPs) to the reviewing Institutional Review Board (IRB).

- Protocol identifying information: protocol title and number, PI’s name, and the IRB project number;
- A detailed description of the event, incident, experience, or outcome;
- An explanation of the basis for determining that the event, incident, experience, or outcome represents an UP;
- A description of any changes to the protocol or other corrective actions that have been taken or are proposed in response to the UP.

To satisfy the requirement for prompt reporting, UPs will be reported using the following timeline:

- UPs that are serious adverse events (SAEs) will be reported to the IRB within 7 days of the investigator becoming aware of the event.
- Any other UP will be reported to the IRB within 14 days of the investigator becoming aware of the problem.
- All UPs should be reported to appropriate institutional officials (as required by an institution’s written reporting procedures), the supporting agency head (or designee), and the Office for Human Research Protections (OHRP) within 31 days of the IRB’s receipt of the report of the problem from the investigator.

## 9 STATISTICAL CONSIDERATIONS

### 9.1 STATISTICAL HYPOTHESES

**Aim 1. Assess whether T2D alters cognitive response to 8 weeks of transdermal estrogen.** Composite z-scores will be calculated by calculating a z-score for each cognitive task and summing z-scores for the tasks designated as Short-Term Memory (STM Composite) and Executive Function (EF Composite). We will assess differences in follow-up scores between intervention groups using ANCOVA after covariate adjustment for baseline scores using SAS software. Because age, BMI, and education may influence changes in cognition over time (e.g. learning effects), we will assess whether including these as

covariates affects results. The primary outcomes will be the composite scores. Secondary analyses will examine individual components.

**Aim 2. Assess whether T2D alters estrogen effects on brain uptake of glucose and ketone bodies in whole brain and Alzheimer's disease (AD) related regions of interest.** FDG and AcAc PET scan data will be analyzed with PMOD® Software using methods described by our collaborators. Briefly, imaging data are co-registered to T1 structural MRI data to conduct region of interest (ROI)-based analyses. This will quantify absolute global and regional uptake of FDG and AcAc to determine uptake, as well as uptake of AcAc relative to FDG to find potential areas of compensatory ketone use. T1 MRI images will be processed using publically available software in a customized workflow, primarily ANTs due to evidence of superior performance. Average values for ROI will be calculated for the posterior cingulate/precuneus, temporal lobe, and prefrontal cortices, as these are regions of observed decreases in FDG uptake in AD and are relevant for development and progression of dementia. Inference will be based the same approaches as for cognitive data for 1) whole-brain glucose uptake, 2) whole-brain ketone uptake, 3) regional glucose uptake, 3) regional ketone uptake, 4) whole-brain ratio of ketone/glucose uptake, and 5) regional ratio of ketone/glucose uptake. We will assess inter-relationships among changes in these outcomes and with changes in cognitive function using principal components and canonical correlation.

**Alternate hypotheses.** In addition to its effects on cellular bioenergetics, estrogen can affect vascular health. A recent finding that women with T2D were at increased dementia risk saw increased risk for vascular dementia. Thus, the interaction between T2D and estrogen may be mediated through vascular effects, or through an interaction between metabolic and vascular effects. Therefore, we have included two MRI scans to assess vascular brain health: 1) a T2-weighted FLAIR image to assess white matter hyperintensities, an indicator of small-vessel disease correlated with diabetes status and hypertension, and 2) a susceptibility-weighted image to assess for microbleeds.

The 3 City Study found interactions between T2D status and endogenous estrogen levels. The WHIMS study observed an interaction between T2D and women randomized to oral estrogen treatment. We will examine exploratory cross-sectional associations between estrogen levels before estrogen administration and PET and cognitive testing to assess for differences due to endogenous estrogen.

Both the WHIMS and 3 City studies statistically adjusted for BMI. To minimize any potential influence of BMI that may persist after BMI adjustment, we plan to limit participants' BMI range and match for BMI. We will also examine whether changes in BMI or diabetes treatment over follow-up affect results. Cortisol may be elevated in older adults with T2D, even after controlling for BMI and the presence of cortisol may modify the effects of estrogen on cognition. Therefore, serum cortisol will be assayed to test for potential interactions between estrogen and cortisol. Due to the cyclical nature of cortisol secretion, all blood draws will occur between 8AM-10AM. OGTT data will allow us to use glucose and insulin levels as covariates as needed. [name] are currently collecting pilot data on methods that may enhance the sensitivity of the [C]AcAc scans. If these methods are successful, they will be incorporated into the final study.

